6.5.7 Anaphylaxis assessment

An adjudication committee (AC) is in place to determine whether cases identified through a search algorithm based on the Standardized MedDRA Queries of hypersensitivity may represent cases of anaphylaxis. Further details regarding the AC will be documented in the AC charter. See [Section 8.5](#) for details.

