1.1 Background

Urticaria is a heterogeneous group of diseases characterized by itchy hives and/or angioedema. Chronic urticaria is defined as urticaria that has been continuously or intermittently present for more than 6 weeks (Maurer, et al 2013, Bernstein, et al 2014). Chronic urticaria is then further divided into two subgroups: Chronic Spontaneous Urticaria (CSU) and Inducible Urticaria (IU) the latter including physical urticaria such as heat-, cold-, or pressure-urticaria, and special variants such as cholinergic urticaria. CSU is defined as spontaneous appearance of itchy wheals, angioedema, or both ≥ 6 weeks due to known or unknown causes (Zuberbier, et al 2014). A combination of both the CSU and an inducible form of urticaria is possible, such as the frequently observed combination of asymptomatic dermographic urticaria and CSU.

Previously, all chronic urticaria forms without a known trigger were named “chronic idiopathic urticaria” (CIU). Due to medical progress it is now known that in some of the previously considered “idiopathic” urticaria forms in fact auto-antibodies may be detected. However, the daily fluctuating appearance of the symptoms in this chronic urticaria with auto-antibodies still remains unpredictable and is not induced by a demonstrable trigger, hence appear spontaneously. In order to reflect in the terminology correctly that some of the former “idiopathic” forms in fact may have detectable auto-antibodies, this population is now referred to as chronic spontaneous urticaria (CSU) according to the international guideline (Maurer, et al 2013, Zuberbier, et al 2014). The use of the expression “chronic idiopathic urticaria” in medical practice is no longer recommended. However, this new naming convention is not implemented in all parts of the world and in countries such as the United States and Canada the patient population with chronic urticaria with a non-specific etiology, or unknown triggers is still referred to as chronic idiopathic urticaria (CIU). Following the International Guideline, the disease entity will be referred to as CSU throughout this document for consistency.

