8.5 Adjudication Committees

To enhance the safety assessment, more specifically relative to anaphylactic events, neoplastic events and major cardio-cerebrovascular events, three independent panels of experts external to Novartis will provide independent reviews of potentially identified events in a blinded manner and adjudicated on a regular basis.

All the details of the adjudication processes including the committee members are included in the adjudication committee charters.

9 Data analysis

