9.4.1 Variable(s)

The primary objective of this study is to obtain additional data on the long-term safety and tolerability of QGE031 for 12 months of treatment in CSU patients.

The primary variables are: for AEs/SAEs, ECGs, laboratory assessments, vital signs data and events of special interest such as hypersensitivity reactions, anaphylaxis, cardio-cerebrovascular events, and pre- and malignancies.

Baseline for the safety analysis is the last visit (Visit 206) of the core study CQGE031C2201, except for parameters which are newly assessed at Visit 301, in which case Visit 301 is the baseline visit.

Adverse events

All adverse events which start after the first dose of study medication in the extension study and within 52 weeks of the last dose will be considered as a treatment emergent adverse event.

Treatment emergent adverse events may be presented in 2 sub-groups; those which started after first study drug dose and within 4 weeks after the last dose and those which started more than 4 weeks after the last dose. Adverse events that started during the follow-up epoch of the core study will be reported and analyzed in the core study and will not be included in tables of the extension study unless they become more severe. They will, however, be included in listings with additional collected information (e.g., outcome) as applicable. Adverse events that started in the core study but became more severe in the extension study will be reported and analyzed as new events.

Treatment emergent adverse events with the number and percentage of patients having any adverse event overall, by system organ class and preferred term will be provided for:

- All adverse events
- Adverse events by maximum severity
- Adverse events suspected by the investigator as study drug-related
- Serious adverse events
- Adverse events leading to permanent discontinuation of study drug

AEs of Special Interest

Hypersensitivity assessment

All hypersensitivity reactions that are possible cases of anaphylaxis will be adjudicated by independent committee. The adjudicated hypersensitivity reactions will be summarized by preferred term and severity.

Cardio- and Cerebrovascular events

All cardio- and cerebrovascular events will be adjudicated by independent committee and summarized by preferred term and severity.

Malignancies

Frequency of adjudicated malignancies whether newly detected or worsening of existing malignancies will be reported.

Laboratory data

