9.4.2 Statistical model, hypothesis, and method of analysis

No hypotheses will be tested.

Adverse events will be summarized by presenting the number and percentage of patients having any AE by primary system organ class and/or preferred term. AE by severity, drug related AEs, AEs leading to premature discontinuation of study drug, death and serious AEs will be presented in a similar format as all AEs.

AEs related to potential anaphylaxis will be summarized separately.

Laboratory and vital sign data will be summarized by presenting summary statistics of values and change from baseline by visit, and by presenting frequency of patients with clinically notable changes.

[figure not shown]
ECG intervals will be summarized by presenting summary statistics for change from baseline values by visit. Count and frequency of clinically notable ECG abnormalities or changes will be presented. The (uncorrected) QT interval will be corrected according to the Fridericia's formulae.

Laboratory data, vital sign data and ECG data will be listed with abnormal value flagged based on normal ranges or clinically notable ranges.

Other safety data will be summarized and listed as appropriate.

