13.3 Appendix 3 World Allergy Organization Grading System

World Allergy Organization subcutaneous immunotherapy systemic reaction grading system

Grade 1	Grade 2	Grade 3	Grade 4	Grade 5
Symptom(s)/sign(s) of 1 organ system present	Symptom(s)/sign(s) of more than 1 organ system present	Lower respiratory	Lower or upper respiratory	Death
Cutaneous	Lower respiratory	Asthma (eg, 40% PEF or FEV1 drop	Respiratory failure with or without loss of consciousness	
Generalized pruritus, urticaria, flushing, or sensation of heat or warmth	or Asthma: cough, wheezing, shortness of breath (eg, less than 40% PEF or FEV1 drop, responding to an inhaled bronchodilator)	or NOT responding to an inhaled bronchodilator)	or without loss of consciousness	
or		Upper respiratory	Cardiovascular	
Angioedema (not laryngeal, tongue or uvular)	responding to an inhaled bronchodilator)	Laryngeal, uvula, or tongue edema with or without stridor	Hypotension with or without loss of consciousness	
or	or			
Upper respiratory	Gastrointestinal			
Rhinitis - (eg, sneezing, rhinorrhea, nasal pruritus and/ or nasal congestion)	Abdominal cramps, vomiting, or diarrhea			
or	or			
Throat-clearing (itchy throat)	Other			
or	Uterine cramps			
Cough perceived to originate in the upper airway, not the lung, larynx, or trachea				
or				
Conjunctival				
Erythema, pruritus or tearing				
Other				
Nausea, metallic taste, or headache				

[figure not shown]
Source: Cox 2010

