2.5.1.1 Adverse events of special interest / grouping of AEs

Adverse events of special interest will be summarized and also will be listed. AEs of special interest include the following, specified as compound-level risk factors defined in the Case Retrieval Strategy (CRS):

- Anaphylaxis (including Hypersensitivity reactions)
- Parasitic (Helminthic) Infection
- [REDACTED]
- Serum Sickness Syndrome/Serum Sickness Like Disease
- Neoplastic conditions
- Eosinophilic Conditions / Churg-Strauss Syndrome
- Arterial Thromboembolic Events (ATEs) / Cardiovascular toxicity
- Injection site reactions
- Thrombocytopenia
- Reduction in Vaccine Efficacy
- Liver Toxicity
- Contraceptive measures

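### The visible SAP pools anaphylaxis with other hypersensitivity and only lists adjudicated events, so it plans no rate for adjudicated anaphylaxis, although the protocol calls for a separate summary

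*Protocol*

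**What the plan says.** **Protocol.** Case finding has two steps. Under 6.5.7 a search supplies candidates and a committee is to "determine whether cases identified through a search algorithm based on the Standardized MedDRA Queries of hypersensitivity may represent cases of anaphylaxis". Under 8.5, "three independent panels of experts external to Novartis will provide independent reviews", in a blinded manner. Two summaries are then promised. Section 9.4.1 says "The adjudicated hypersensitivity reactions will be summarized by preferred term and severity", and 9.4.2 says "AEs related to potential anaphylaxis will be summarized separately". Section 9.4.1 also names hypersensitivity reactions and anaphylaxis as two separate primary variables.

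**SAP.** Section 2.5 repeats the two as separate variables. Section 2.5.1.1 says "Adverse events of special interest will be summarized and also will be listed", but its visible entry for this risk is a single category, "Anaphylaxis (including Hypersensitivity reactions"), defined by a Case Retrieval Strategy that is not part of the documents. One other entry in that list is blacked out. Section 2.5.1.2 lists adjudicated hypersensitivity reactions and flags the treatment-emergent ones. Section 4 declares that adjudicated AEs are listed and not summarized because few are expected. Section 2.5.1 gives n (%) of all treatment-emergent AEs by system organ class and preferred term, overall and for the treatment epoch.

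**The concern.** Hypersensitivity, including anaphylaxis, is the known safety issue that protocol 3.6 names, and one anaphylaxis case in another QGE031 extension study is reported there. Long-term safety is the primary objective. A reader of the study report will want one number: how many patients had anaphylaxis as judged by the independent panel, with its uncertainty. The visible SAP does not produce it. The only special-interest frequency that contains anaphylaxis is pooled with milder reactions.

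The disease makes pooling more awkward than usual. According to protocol 1.1, "CSU is defined as spontaneous appearance of itchy wheals, angioedema, or both". Protocol Appendix 3 counts "Generalized pruritus, urticaria, flushing, or sensation of heat or warmth" among grade 1 systemic reactions, together with non-laryngeal angioedema. The AE definition in protocol 7.1 does not exclude CSU symptoms. A disease flare recorded as an AE could therefore enter the same category as an anaphylactic reaction.

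**Working it through.** **1. Promised and planned outputs side by side**

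| Output | Protocol | Visible SAP |
|---|---|---|
| Potential anaphylaxis, separate summary | 9.4.2: yes | 2.5.1.1: pooled category only; no visible declaration of a change |
| Adjudicated reactions by preferred term and severity | 9.4.1: yes | 2.5.1.2: flagged listing; change declared in Section 4 |
| n (%) of adjudicated anaphylaxis | obtainable from the 9.4.1 summary if the result is shown | none |
| Reported AEs by preferred term | 9.4.1: yes | 2.5.1: yes, before adjudication |

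**2. Scale of the event count.** Input: N of about 240 (protocol 9.7). The values in protocol Figure 9-1 are not shown, so there is no stated figure to reproduce. The same quantity, P(at least one event) = 1 − (1 − p)^N, at N = 240 is:

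- p = 0.1%: 1 − 0.999^240 = 21.3%
- p = 0.5%: 1 − 0.995^240 = 70.0%
- p = 1%: 1 − 0.99^240 = 91.0%

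Expected counts are 240 × p = 0.24, 1.2 and 2.4. At incidences of this order, none to a few cases is the realistic scale.

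**3. Anaphylaxis on its own line** (Clopper-Pearson 95%, N = 240)

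- 0 cases: 0%; upper limit 1 − 0.025^(1/240) = 1.5%
- 1 case: 1/240 = 0.42%; lower limit 1 − 0.975^(1/240) = 0.01%, upper limit 2.3%
- 2 cases: 2/240 = 0.83%; 0.10% to 2.98%

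**4. The same single case inside a pool.** The documents give no rate for other hypersensitivity events. Assumption, for illustration: 2% to 20% of patients have such an event, and none of them is the anaphylaxis patient.

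| Assumed background | Pool | Pool rate (95% CI) | Anaphylaxis share of pool |
|---|---|---|---|
| 2% (5 patients) | 6/240 | 2.5% (0.9 to 5.4) | 1/6 = 17% |
| 5% (12) | 13/240 | 5.4% (2.9 to 9.1) | 1/13 = 8% |
| 10% (24) | 25/240 | 10.4% (6.9 to 15.0) | 1/25 = 4% |
| 20% (48) | 49/240 | 20.4% (15.5 to 26.1) | 1/49 = 2% |

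With two cases the share is 2/7 = 29% at 2% background and 2/50 = 4% at 20%. Across this range the pooled rate says little about anaphylaxis: moving from no case to one changes it by only 0.42 percentage points.

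**5. CSU symptoms in the pool.** Three texts make this possible: the disease definition (protocol 1.1), the overlapping reaction signs (Appendix 3) and an AE definition with no CSU exclusion (7.1). The texts do not fix which terms the retrieval strategy selects, or how often sites record flares as AEs. No rate can be derived, so none is given.

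**The case against.** - **The search is sound.** A broad search followed by blinded external adjudication is a sensitive way to find cases. This stands in full. The gap is in what the SAP reports afterwards.
- **Cases stay visible.** The listing shows every adjudicated reaction, and an event coded to an anaphylaxis preferred term has its own line in the tables of SAP 2.5.1, including those for serious and drug-related events. A reader might infer that pooling hides an anaphylaxis signal; the documents do not support that. What remains is narrower: those tables show terms as reported, and a listing gives no rate or interval.
- **Listing only is declared and reasoned.** True for adjudicated AEs. But a small expected count does not remove the need for a rate: zero of 240 is informative, because it bounds the incidence at 1.5%.
- **Protocol 9.4.2 speaks of potential anaphylaxis.** A dedicated special-interest category could be read as that summary, so the conflict is arguable. Still, a category that includes hypersensitivity reactions in general is hard to call a separate summary, and SAP 2.5 itself names the two apart.
- **A single table row is an inference.** There is no table shell, and the retrieval strategy may have sub-levels. If it does, one sentence in the SAP settles this part.
- **Appendix 3 does not define the search.** Correct: the protocol uses it for a treatment-discontinuation rule (5.6.2). Here it shows only that the signs overlap. A reader might go further and conclude that the pooled frequency would mainly measure CSU flares; that needs relapse and recording rates that the documents do not contain.

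**Conclusion.** The point holds as a reporting gap. The visible SAP plans no n (%) for adjudicated anaphylaxis, and its only special-interest frequency containing anaphylaxis is pooled with other hypersensitivity. The departure from protocol 9.4.1 is declared. The pooled category and the loss of the separate summary in 9.4.2 are not declared in any visible entry; blacked-out entries in Section 4 could contain it.

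The effect is dilution of a summary rate, not loss of cases. Its size depends on an assumed background: one case in 240 would be 17% of the pool at 2% and 2% of it at 20%. Contamination by CSU hives and angioedema is possible but unquantified, and it depends on the Case Retrieval Strategy. The change is worth making because safety is the primary objective and the remedy is cheap.

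**What to change.** In SAP 2.5.1.1 and 2.5.1.2:

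1. Report treatment-emergent adjudicated anaphylaxis on its own line, as n (%) with an exact 95% CI. On a second line, report potential anaphylaxis, defined as the cases sent to adjudication.
2. Report other hypersensitivity reactions separately. Show the urticaria, angioedema and pruritus preferred terms as a sub-line, by preferred term. Do not remove events because an investigator attributes them to CSU: that attribution is not among the AE items in protocol 7.1, and in an open-label study it could move real drug reactions out of the group.
3. Show these lines overall and for the treatment epoch, as SAP 2.5.1 does for treatment-emergent AEs.
4. Record the pooled category, or its replacement, in SAP Section 4.

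Cost: SAP wording and a few more table lines with low counts. Preferred terms and adjudication results are already collected under the plan, so no new data are needed. If the retrieval strategy already separates these groups, a sentence saying so covers the separation; the adjudicated line must still be added.

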6.5.8 Assessment of cardio-cerebrovascular events

[figure not shown]
[figure not shown]
An AC is in place to review all cases identified through a search algorithm based on the Standardized MedDRA Queries of cardio-cerebrovascular events. The clinical presentation and association of these events with pre-existing risk factors will be part of the assessment. See [Section 8.5](#) for details.

[figure not shown]
[figure not shown]
6.5.9 Assessment of pre-malignancies and malignancies

[figure not shown]
An AC will be put in place to review all cases identified through a search algorithm based on the Standardized MedDRA Queries of pre-malignancies and malignancies. The clinical presentation and association of these events with pre-existing risk factors will be part of the assessment. See [Section 8.5](#) for details.

6.5.10 Appropriateness of safety measurements

Events of special interest such as suspected anaphylaxis, neoplastic events, and cardiovascular events will be monitored and will be adjudicated by expert adjudication committees.

7 Safety monitoring

7.1 Adverse Events

An adverse event (AE) is any untoward medical occurrence (i.e., any unfavorable and unintended sign [including abnormal laboratory findings], symptom or disease) in a patient or clinical investigation patient after providing written informed consent for participation in the study. Therefore, an AE may or may not be temporally or causally associated with the use of an investigational product.

For all patients who have signed informed consent and are entered into the next epoch (Extension 1 Treatment epoch) of the study, all adverse events occurring after informed consent is signed will be recorded on the Adverse Event CRF.

The occurrence of adverse events should be sought by non-directive questioning of the patient at each visit during the study. Adverse events also may be detected when they are volunteered by the patient during or between visits or through physical examination, laboratory test, or other assessments.

Abnormal laboratory values or test results constitute adverse events only if they fulfill at least one of the following criteria:

- they induce clinical signs or symptoms,
- they are considered clinically significant,
- they require therapy.

Clinically significant abnormal laboratory values or test results should be identified through a review of values outside of normal ranges/clinically notable ranges, significant changes from baseline or the previous visit, or values which are considered to be non-typical in patient with underlying disease. Investigators have the responsibility for managing the safety of individual patient and identifying adverse events. Alert ranges for labs and other test abnormalities are included in [Appendix 1](#) and will be described in the laboratory manual.

Adverse events should be recorded in the Adverse Events CRF under the signs, symptoms or diagnosis associated with them, accompanied by the following information:

- the severity grade
 - mild: usually transient in nature and generally not interfering with normal activities
 - moderate: sufficiently discomforting to interfere with normal activities
 - severe: prevents normal activities
- its relationship to the investigational treatment (no/yes), or
- its duration (start and end dates) or if the event is ongoing an outcome of not recovered/not resolved should be reported.
- whether it constitutes a SAE (see [Section 7.2.1](#) for definition of SAE)
- action taken regarding investigational treatment.

All adverse events should be treated appropriately. Treatment may include one or more of the following:

- no action taken (i.e. further observation only)
- investigational treatment dosage adjusted/temporarily interrupted
- investigational treatment permanently discontinued due to this adverse event
- concomitant medication given
- non-drug therapy given
- patient hospitalized/patient's hospitalization prolonged
- its outcome (not recovered/not resolved; recovered/resolved; recovering/resolving, recovered/resolved with sequelae; fatal; or unknown)

Once an adverse event is detected, it should be followed until its resolution or until it is judged to be permanent, and assessment should be made at each visit (or more frequently, if necessary) of any changes in severity, the suspected relationship to the study drug, the interventions required to treat it, and the outcome.

Information about common side effects already known about the investigational drug can be found in the Investigator Brochure (IB) or will be communicated between IB updates in the form of Investigator Notifications. This information will be included in the patient informed consent and should be discussed with the patient during the study as needed.

The investigator should also instruct each patient to report any new adverse event (beyond the protocol observation period) that the patient, or the patient's personal physician, believes might reasonably be related to study treatment. This information should be recorded in the

investigator's source documents; however, if the AE meets the criteria of an SAE, it must be reported to Novartis.

7.2 Serious adverse events

7.2.1 Definition of SAE

An SAE is defined as any adverse event (appearance of (or worsening of any pre-existing) undesirable sign(s), symptom(s) or medical conditions(s) which meets any one of the following criteria:

- is fatal or life-threatening
- results in persistent or significant disability/incapacity
- constitutes a congenital anomaly/birth defect
- requires inpatient hospitalization or prolongation of existing hospitalization, unless hospitalization is for:
 - routine treatment or monitoring of the studied indication, not associated with any deterioration in condition (specify what this includes)
 - elective or pre-planned treatment for a pre-existing condition that is unrelated to the indication under study and has not worsened since signing the informed consent
 - treatment on an emergency outpatient basis for an event not fulfilling any of the definitions of a SAE given above and not resulting in hospital admission
 - social reasons and respite care in the absence of any deterioration in the patient's general condition
- is medically significant, i.e. defined as an event that jeopardizes the patient or may require medical or surgical intervention.

[figure not shown]
All malignant neoplasms will be assessed as serious under “medically significant” if other seriousness criteria are not met.

Life-threatening in the context of a SAE refers to a reaction in which the patient was at risk of death at the time of the reaction; it does not refer to a reaction that hypothetically might have caused death if more severe (see Annex IV, ICH-E2D Guideline).

Medical and scientific judgment should be exercised in deciding whether other situations should be considered serious reactions, such as important medical events that might not be immediately life threatening or result in death or hospitalization but might jeopardize the patient or might require intervention to prevent one of the other outcomes listed above. Examples of such events are intensive treatment in an emergency room or at home for allergic bronchospasm, blood dyscrasias or convulsions that do not result in hospitalization or development of dependency or abuse (see Annex IV, ICH-E2D Guideline).

Any suspected transmission via a medicinal product of an infectious agent is also considered a serious adverse reaction.

All AEs (serious and non-serious) are captured on the CRF, SAEs also require individual reporting to DS&E as per [section 7.2.2](#)

